The protocol, informed consent form(s), recruitment materials, and all participant materials will be submitted to the IRB for review and approval. Approval of both the protocol and the consent form must be obtained before any participant is enrolled. Any amendment to the protocol will require review and approval by the IRB before the changes are implemented to the study. All changes to the consent form will be IRB approved; a determination will be made regarding whether a new consent needs to be obtained from participants who provided consent, using a previously approved consent form.

Confidentiality Statement

This document is confidential and is to be distributed for review only to investigators, potential investigators, consultants, study staff, and applicable independent ethics committees or institutional review boards. The contents of this document shall not be disclosed to others without written authorization from WCM, unless disclosure on ClinicalTrials.gov is federally required.

Institution Name

Principal Investigator's Name

Principal Investigator's Signature

Date

List of Abbreviations

AE	Adverse Event
CFR	Code of Federal Regulations
CRF	Case Report Form
CTSC	Clinical Translational Science Center
DSMB	Data Safety Monitoring Board
DSMP	Data Safety Monitoring Plan
FDA	Food and Drug Administration
GCP	Good Clinical Practice
HIPAA	Health Insurance Portability and Accountability Act of 1996
HRBFA	Human Research Billing Analysis Form
HUD	Humanitarian Use Device
ICF	Informed Consent Form
IDE	Investigational Device Exemption
IND	Investigational New Drug
IRB	Institutional Review Board
PHI	Protected Health Information
PI	Principal Investigator
REDCap	Research Electronic Data Capture
SAE	Serious Adverse Event
SUSAR	Suspected Unexpected Serious Adverse Reaction
UIRTSO	Unanticipated Problem Involving Risks to Subjects or Others
WCM	Weill Cornell Medicine

1. Protocol Summary

Full Title:	Assessing the Hemostatic Efficacy of Pathogen Reduced Platelets in Children Undergoing Cardiopulmonary Bypass Surgery: A Pilot Clinical Trial
Short Title:	Hemostatic Efficacy of Pathogen Reduced Platelets
Clinical Phase:	IV
Principal Investigator:	[name], MS
Study Description:	This is a pilot clinical trial to assess the post-operative bleeding in children who receive pathogen-reduced (PR) platelet transfusions versus standard (large volume delayed sampling – LVDS) platelet transfusions both during and for 24 hours following cardiopulmonary bypass surgery.
Sample Size:	126 (63 per group)
Enrollment:	This study will enroll approximately 252 subjects and screen up to 500 subjects. Though the sample size is 126, since the decision to transfuse platelets is at the discretion of the clinical team, and our preliminary data shows approximately 50% of children are transfused, we will need to enroll double the sample size, or 252 children (see full protocol for further explanation).
Study Population:	Children (ages 0-18 years of age) undergoing cardiopulmonary bypass surgery
Enrollment Period:	Length of hospitalization
Study Design:	This is an open label, randomized clinical trial of children undergoing cardiopulmonary bypass surgery at either Komansky Children's Hospital/Weill Cornell or Morgan Stanley Children's Hospital/Columbia. For children who require platelet transfusions either intra or post-operatively for the first 24 hours (decision to transfuse left at discretion of clinical team), they will receive either all PR or all LVDS platelet transfusions. Bleeding from the surgically placed chest tube will be recorded per hour for the first 24 hours post-operatively. In addition, the total volume of transfusion of any blood products will be recorded.
Description of Sites/ Facilities Enrolling Participants:	Komansky Children's Hospital/Weill Cornell and Morgan Stanley Children's Hospital/Columbia.
Study Duration:	6/30/2024
Participant Duration:	Length of hospitalization (no follow-up visits necessary)
Study Agent/Device Name	
Intervention Description:	Both PR and LVDS platelets are considered standard of care (currently whatever product is available is dispensed by transfusion medicine services). Platelets will be transfused in doses of 10mL/kg.

[figure not shown]
Primary Objective: To determine the amount of post-operative bleeding in children receiving PR versus LVDS platelet transfusions during and following cardiopulmonary bypass surgery

Secondary Objectives: To determine the blood product requirements and nosocomial infections in children receiving PR versus LVDS platelet transfusions during and following cardiopulmonary bypass surgery

Primary Endpoints: Chest tube output for first 24 hours following cardiopulmonary bypass surgery

Secondary Endpoints: Total dose red blood cell transfusions in first 48 hours, Total blood products transfused (intra and post-operatively) in first 48 hours, nosocomial infections

1.1 Schema

1.2 Study Objectives and End Points

1.2.1 Primary Objectives

To determine the amount of post-operative bleeding in children receiving PR versus LVDS platelet transfusions during and following cardiopulmonary bypass surgery.

1.2.2 Secondary Objectives

To determine the blood product requirements and nosocomial infections in children receiving PR versus LVDS platelet transfusions during and following cardiopulmonary bypass surgery.

1.2.3 Exploratory Objectives

Not applicable

1.2.4 Primary Endpoints

Chest tube output for first 24 hours following cardiopulmonary bypass surgery

1.2.5 Secondary Endpoints

Total dose red blood cell transfusions in first 48 hours, total blood products transfused (intra and post-operatively) in first 48 hours, nosocomial infections

2. Background

2.1 Disease

Pediatric patients undergoing cardiopulmonary bypass (CPB) are at high risk of ongoing bleeding due to hemodilution, platelet dysfunction, hypothermia and anti-coagulation [1]. Therefore, they often require post-operative hemostatic blood component transfusions, most commonly platelet transfusions, in order to prevent to stop bleeding [2, 3]. These children represent a unique patient population in that they each have mediastinal and/or pleural drains placed intra-operatively and therefore, their post-operative bleeding is quantifiable.

2.2 Investigational Agent/Device, or Surgical Treatment/Method

Platelet transfusions are frequently prescribed to children to prevent or treat bleeding, but have been associated with increased transfusion reactions, as compared to their adult counterparts [4], as well as increased mortality [5]. Though red blood cells (RBCs) and plasma must be stored at lower temperatures, platelets are traditionally stored at room temperature with gentle agitation. Such conditions incur the additional risk of microbial contamination [6, 7]. To combat this, pathogen-reduced (PR) platelets, treated with either riboflavin or amotosalen and then exposed to ultraviolet illumination, have been developed [8, 9]. Studies have demonstrated that PR technology inactivates infectious agents [10] and lymphocytes [11]. In adult patients, PR platelets have been linked to increased platelet refractoriness and decreased platelet correct count increments, but no clinically significant

bleeding or increased risk of serious adverse events [12, 13].

Similar studies in the pediatric population have been limited. In an observational study of cohort of 240 neonates and children, patients who received PR platelets had an overall increase in total transfusion need as compared to those receiving non-PR platelets [14]. In a smaller cohort of children with oncologic diagnoses, those who received PR platelets had lower incremental increases in their platelet count following transfusion, but no significant increase in bleeding events [15]. The hemostatic efficacy of PR platelets has not been sufficiently examined in pediatric patients, particularly in those with ongoing bleeding.

Given the increased safety of PR platelets in regard to transfusion transmitted infections, the FDA encouraged all transfusion medicine services to provide either PR platelets or LVDS platelets to all patients in guidance issued in 2017. The transfusion medicine services at New York Presbyterian Hospital (on both the Weill Cornell and Columbia campuses) began introduction of PR platelets into the inventory in 2017 and maintain an inventory of both PR platelets and LVDS platelets currently. There is no difference in the risk of infection between PR and LVDS platelet products.

2.3 Rationale

Given the lack of evidence of hemostatic efficacy of PR platelets in children, we are seeking to characterize the hemostatic efficacy of PR platelets by comparing post-operative bleeding in children undergoing CPB who receive PR versus LVDS platelet transfusions.

2.4 Risk/Benefit Assessment

2.4.1 Known Potential Risks

The need for the transfusion of any blood component, including platelet transfusions, will be at the discretion of the clinical team. Therefore, this study will not put an individual subject at increased risk of receiving a transfusion. In addition, if the platelet product to which the patient is assigned is not available, the patient will receive the available product without delay. Therefore participation in the study does not place the subject at risk of delayed transfusion.

The transfusion of any blood component carries the risk of transfusion transmitted infections, allergic reactions, transfusion associated acute lung injury, transfusion associated circulatory overload and transfusion related immunomodulation. However, these risks are known for both PR and LVDS products so that participation in the study, in which the subject will be randomized to either all PR or all LVDS platelet transfusions during cardiopulmonary bypass surgery and following for 24 hours, poses no increased risk as compared to not participating in the study.

PR platelets have been associated with a lower incremental rise in platelet count following a transfusion as compared to LVDS platelets in children with cancer. Therefore, subjects in this study are at risk of having a lower incremental rise in their platelet count if they receive PR platelets as compared to LVDS platelets. However, since platelets are transfused in the cardiac population not because of thrombocytopenia

but rather platelet dysfunction, this difference in platelet count should not affect the subjects' risk of bleeding.

It is unknown if either product (PR or LVDS platelet transfusions) is less efficacious in hemostasis, i.e. if one product leads to less bleeding.

De-identified clinical information (demographics, surgical characteristics, details regarding the platelet transfusion and clinical outcomes) will be collected on each subject. Though de-identified, there remains a risk of loss of confidentiality.

2.4.2 Known Potential Benefits

Both the FDA and the transfusion medicine services at Weill Cornell and Columbia Universities have determined that both PR platelets and LVDS platelets are equal in potential benefit of decreased transfusion transmitted infections.

Though it is unknown if one product is associated with improved hemostasis, if one product is, the subjects have the potential benefit of decreased bleeding.

2.4.3 Assessment of Potential Risks and Benefits

Given the minimal risks associated with this study (since the transfusions would be given regardless of participation in the study, the study is only ensuring a patient receives all PR or all LVDS platelets), the benefits of possible improved hemostasis, as well as the benefit to society, facilitating a greater understanding of the hemostatic efficacy, outweigh the risks.

2.5 Correlative Studies Background

Not applicable

3. Study Design

3.1 Overall Design

This is a multisite, open-label, randomized trial of PR versus LVDS platelet transfusions in children undergoing cardiopulmonary bypass surgery. The study will be conducted at Komansky Children's Hospital at Weill Cornell and Morgan Stanley Children's Hospital at Columbia. Given that both products are FDA approved and already used in this patient population, it is a Phase IV study. Based on our preliminary retrospective data, we hypothesize that both products will have equivalent hemostasis, as measured by chest tube output in the first 24 hours, as well as total blood component requirements. Given the complexity of surgery is associated with bleeding risk, the two groups will be stratified on a validated score of surgical complexity (STS scoring). All subjects will be enrolled in the study for the length of their hospitalization.

The need for platelet transfusion will not be dictated by the study intervention, but rather the clinical team (both in the operating room and post-operatively, in the pediatric intensive care unit). Given that we do not want to delay the release of blood products from the blood bank, but rather have them available as standard of care in the operating

room, we cannot randomize the subjects at the time of the decision to transfuse platelets. Therefore, we will randomize subjects before the day of surgery. We recognize that there will be a significant number of randomized subjects (approximately 50%) who do not receive a platelet transfusion. Data will be collected on this group and analyzed both separately, and in an intention to treat model.

All platelet transfusions will be given as 10mL/kg as is considered standard of care.

Given the need to cross-check any transfusion of the blood component for patient safety, no area of the labeling will be disturbed and therefore the clinicians caring for the patients will be unblinded. Those responsible for data entry and data analysis will be blinded to the assigned groups of the subjects.

To minimize bias, we will perform subgroup analyses of neonates versus all other children given that the neonatal coagulation system is still under development and different than the coagulation system of the older child.

3.2 Scientific Rationale for Study Design

Limited data exists regarding the hemostatic efficacy of PR platelets in children. Our preliminary data, a retrospective study of 140 children undergoing cardiopulmonary bypass surgery, suggests that PR platelets are equally efficacious in terms of post-operative bleeding, as compared to non-PR platelets. However, retrospective studies are limited, and prospective randomized studies are needed to truly assess the primary outcome (the hemostatic efficacy).

3.3 Justification for Dose

Not applicable (the transfusions will be dosed equally as 10mL/kg as per standard of care)

3.4 End of Study Definition

A participant is considered to have completed the study if he or she has been discharged from the hospital.

4. Subject Selection

4.1 Study Population

Children undergoing cardiopulmonary bypass surgery who meet the inclusion and exclusion criteria will be eligible for participation in this study.

4.2 Inclusion Criteria

1. Male or female 0-18 years of age
2. Undergoing elective cardiopulmonary bypass surgery
3. Are planned to have a chest tube placed in the operating room prior to chest closure

4.3 Exclusion Criteria

1. > 18 years of age
2. Preterm infants (less than 38-week gestational age at time of surgery)
3. On extracorporeal membrane oxygenation (ECMO) or ventricular assist device prior to surgery
4. Family requests limitation of blood products (i.e. Jehovah's Witness)
5. Congenital bleeding disorder
6. Are planned to require ECMO post-op
7. Previously enrolled in the study

4.4 Lifestyle Considerations

Not applicable

4.5 Screen Failures

Screen failures are defined as participants who consent to participate in the clinical trial but are not subsequently randomly assigned to the study intervention or entered in the study. Demographics, screen failure details, and eligibility criteria will be collected on these individuals.

Though children undergoing elective cardiopulmonary bypass surgery do so only once during the course of 18 months (which will be the length of subject recruitment for this study), if a participant does meet inclusion criteria twice (undergoes a second elective cardiopulmonary bypass surgery in the course of 18 months), he/she can be rescreened and re-enrolled.

4.6 Strategies for Recruitment and Retention

All children scheduled to undergo elective cardiopulmonary bypass surgery are seen in the outpatient cardiothoracic (CT) surgery clinic setting approximately 3-5 days prior to surgery. Subjects and their families will be approached for assent/consent at this outpatient visit. Clinical staff at these outpatient sites (at Komansky Children's Hospital at Weill Cornell and Morgan Stanley Children's Hospital at Columbia) will be educated on the inclusion/exclusion criteria and consenting process. They will introduce the study to the families and if willing, the families will be approached by a clinical research coordinator for consent. The number of subjects eligible as well as those enrolled will be logged and reviewed on a monthly basis.

For neonates admitted for their birth and awaiting cardiac surgery, they will be approached in the neonatal intensive care unit by the CT surgery team. The families will be introduced to the study by the CT surgery team and if willing, will be approached by a clinical research coordinator for consent.

Subjects will be enrolled regardless of gender, race, and ethnicity. To demonstrate a difference of 1 mL/kg/hr of post-operative bleeding between the two study groups with 80% power, we will need 126 subjects enrolled and transfused platelets (63 subjects/group). Given the need for randomization prior to the decision to transfuse (as described above in Section 3.1), and the estimate that 50% of patients will not require any platelet transfusions,

we will need to consent and randomize approximately 252 subjects. Given that the two centers perform approximately 500 surgeries per year and the enrollment period will be approximately 18 months, we will require a consent rate of 34%.

We seek to enroll only children, who are considered a vulnerable participant, in order to understand the hemostatic efficacy of PR platelet transfusions in this population. The coagulation systems of infants and children are unique to adults and therefore children must be studied separately. Participants and/or their families will no be compensated for participation in the study.

5. Registration Procedures

5.1 Subject Registration (WCM only)

Subjects will be registered within the WRG-CT as per the standard operating procedure for Subject Registration.

5.2 Subject Registration (Sub-sites)

Subjects will be registered as per the standard operating procedure for Subject Registration at Columbia. All data will be collected in a de-identified manner within REDCap hosted by Weill Cornell."

6. Study Procedures

6.1 Schedule of Assessments

Table 1. Schedule of trial events

	Pre-Operative Visit	Operative Course	Post-Op Day 0	Post-Op Day 1	Post-Op Day 2	Off Study
Platelet Transfusion	Given at discretion of clinical team (group assignment to be maintained only through first 24 hours post-operatively)					
Informed Consent	X					
Demographics	X					
Medical History	X					
Physical Exam*	X		X	X	X	
Vital Signs*	X	X	X	X	X	
Weight*			X	X	X	
CBC*		X	X	X	X	

PT/PTT, fibrinogen*		X	X			
Outcome Evaluation		X	X	X	X	X
Medical Record Review and Data Collection		X	X	X	X	X
Adverse Event Assessment		X	X	X	X	

*all collected regularly as standard of care

6.1.1 Screening Visit

All children who are going elective cardiopulmonary bypass surgery are seen approximately 3-5 days in the CT surgery outpatient clinic as standard of care. This visit will also serve as the screening visit for these children. All neonates who are going elective cardiopulmonary bypass surgery during their birth admission are seen 2-3 days prior to surgery by the CT surgery team in the NICU. This consultation will also serve as the screening visit for these children. At this visit/consultation, the following events will occur:

- *Informed consent*
- *Demographics*
- *Medical history*
- *Physical exam*
- *Vital signs*

Once consented, randomization will occur at this phase, to allow for ordering from the New York Blood Center and so as not to delay the release of the platelet transfusion from the blood bank during the treatment phase. Eligible subjects will be randomly assigned to either PR or LVSD platelets (should they need a platelet transfusion) in a 1:1 ratio using a computer-generated randomization scheme stratified by surgical complexity (STS score) as developed by the statistical team.

6.1.2 Treatment Phase

Subjects will receive platelet transfusion(s) in the group to which they were randomized (PR vs LVDS) at the discretion of the clinical team for the time they are in the operating room through the first 24 hours post-operatively.

6.1.2.1 Operative Course

Data regarding the operative course, including vital signs, receipt of any hemostatic medications or blood products will be collected from the operative course. In addition, information regarding standard of care laboratory testing will be obtained. Of note, if testing is not performed as per standard of care, we will not obtain the laboratory assays only for the purpose of the study. Lastly, chest tube output in the OR and any adverse events in the OR will be collected. In summary, the following events will be recorded:

- *Vital Signs*
- *CBC, PT/PTT, fibrinogen (as obtained per standard of care)*

- *Outcome Evaluation*
- *Medical Record Review and Data Collection*
- *Adverse Events Assessment*

6.1.2.2 Post-Op Days 0-2

Because the primary outcome is the chest tube output in the first 24 hours, the intervention (PR versus LVDS platelet transfusions) will only be maintained for the first 24 hours post-op. In other words, if a subject requires a platelet transfusion after the first 24 hours post-op, they can receive whichever product is next available in the blood bank. During post-op days 0-2, the following events will be recorded:

- *Vital Signs*
- *Physical Exam*
- *CBC, PT/PTT, fibrinogen (as obtained per standard of care)*
- *Outcome Evaluation*
- *Medical Record Review and Data Collection*
- *Adverse Events Assessment*

6.1.3 Follow-up Phase

Subjects will be followed through the time of discharge to determine the following clinical outcomes: Mechanical ventilation free days, vasoactive free days, PICU free days, nosocomial infections, and in-hospital mortality. All “free days” will be calculated from the days a patient is alive in the PICU with 28-day max (i.e. a patient who is in the PICU for 10 days and ventilated for 4 days will have 3 mechanical ventilation free days, a patient who is in the PICU 30 days and ventilated 2 days will have 26 mechanical ventilation free days, and a patient who dies in the PICU on day 2 being mechanically ventilated the entire time will have 0 mechanical ventilation free days). All patients will be considered off study at time of hospital discharge. The following events will be recorded during the follow-up phase:

- *Outcome Evaluation*
- *Medical Record Review and Data Collection*

7. Study Intervention

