10.4 Other Response Parameters

Though not directly related, clinical outcomes, such as mortality, length of hospital stay, length of PICU stay, length of mechanical ventilation and length of vasoactive therapy will be collected.

11. Data Reporting / Regulatory Considerations

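### The free-days rule in Section 6.1.3 does not reproduce its own first example and, on its natural reading, gives 0 PICU-free days for any stay up to 28 days, credits slower PICU discharge and leaves death unscored

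*Combined protocol and SAP*

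**What the plan says.** Section 6.1.3 (Follow-up Phase) names mechanical ventilation-, vasoactive- and PICU-free days among the outcomes followed to discharge. All three "will be calculated from the days a patient is alive in the PICU with 28-day max". It then gives three worked examples, all about ventilation:

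- The first states a result of 3: "a patient who is in the PICU for 10 days and ventilated for 4 days will have 3 mechanical ventilation free days".
- The second takes a 30-day PICU stay with 2 ventilated days and states a result of 26.
- The third is a death: "a patient who dies in the PICU on day 2 being mechanically ventilated the entire time will have 0 mechanical ventilation free days".

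No other section defines these counts. No formula is written, there is no example for PICU-free or vasoactive-free days, and there is no general statement of how a death is scored. Observation stops at discharge: "All patients will be considered off study at time of hospital discharge" (6.1.3), and likewise "A participant is considered to have completed the study if he or she has been discharged from the hospital" (3.4).

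Free days are not endpoints. Section 1.2.5 lists the secondary endpoints as "Total dose red blood cell transfusions in first 48 hours, total blood products transfused (intra and post-operatively) in first 48 hours, nosocomial infections", and Section 12.4 analyses only those and chest tube output. Section 10.4 adds that mortality, hospital stay, "length of PICU stay, length of mechanical ventilation and length of vasoactive therapy will be collected".

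**The concern.** A free-days count is meant to reward time alive and off support, and to place a death at the bottom of the scale. Counting only days spent in the PICU undermines that. Time after PICU discharge, normally the best outcome, earns nothing, and PICU-free days become PICU days minus PICU days. Death gets no separate score. One of the three examples also disagrees with the rule it illustrates, so a programmer cannot use the examples to find the intended definition.

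At stake is any by-arm summary of these outcomes. If one platelet product delayed PICU discharge without changing ventilation, that arm would show more ventilation-free days. Two programmers could also derive different values for the same child.

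**Working it through.** **Inputs.** The base (days alive in the PICU, 28-day maximum) and the three examples come from Section 6.1.3. Two candidate definitions are compared:

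- A, the natural reading: min(PICU days alive, 28) − days on support. The subtraction is inferred from the text and examples.
- B, a fixed count: 28 − days on support, with death scored 0. This is a comparator and is not stated in the documents.

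**Step 1: the plan's own examples.**

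| Example | Stated | A | B |
|---|---|---|---|
| PICU 10 days, ventilated 4 | 3 | 10 − 4 = 6 | 28 − 4 = 24 |
| PICU 30 days, ventilated 2 | 26 | min(30, 28) − 2 = 26 | 28 − 2 = 26 |
| Death on day 2, ventilated throughout | 0 | 2 − 2 = 0 | 0 (death) |

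Under A, the second example shows that the cap falls on the base; capping the result would give min(30 − 2, 28) = 28. The first example fits neither definition. Day-counting conventions do not rescue it under A: moving one duration by a day gives 5 to 7, and moving both gives 4 to 8.

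**Step 2: PICU-free days under A.** For a stay of P days up to 28, P − P = 0. For 30 days the result is 28 − 28 = 0 if both terms are capped, or 28 − 30 = −2 if only the base is. Under B, survivors with stays of 3, 10, 20 and 28 days score 25, 18, 8 and 0.

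**Step 3: equal support, different PICU stay.** With 2 ventilated days:

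| PICU stay (days) | A | B (survivor) |
|---|---|---|
| 3 | 3 − 2 = 1 | 26 |
| 10 | 10 − 2 = 8 | 26 |
| 20 | 20 − 2 = 18 | 26 |
| 28 | 28 − 2 = 26 | 26 |

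Under A each extra PICU day up to day 28 adds one free day. Vasoactive-free days behave the same way.

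**Step 4: death, with 4 ventilated days.**

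- Death on PICU day 10: A gives 10 − 4 = 6; B gives 0.
- Survivor with a 10-day PICU stay: A also gives 6.
- Survivor leaving the PICU on day 5: A gives 5 − 4 = 1; B gives 28 − 4 = 24.

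The plan's death example cannot show whether a death rule exists, because subtraction alone already gives 0 for a child ventilated throughout.

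**The case against.** The strongest reply is that definition A is a reconstruction. The plan writes no subtraction, and a reading that makes a named outcome 0 for nearly any stay may not be what the authors meant. They may have intended the fixed count, with death scored 0. That stands as a caution about intent. It does not rescue the text, which gives the PICU-day base for all free days, while the fixed count also fails the first example (24 against 3).

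A second reply is that the 3 is a typing slip. It may be. Correcting it to 6 would leave the PICU-free, discharge and death problems in place.

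A third reply is that nothing important depends on these counts. That largely stands. They are outside the primary and secondary endpoints, Section 1.2.3 lists no exploratory objectives, and no test is planned. Raw durations and mortality would expose the pattern.

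A reader might also infer more than the documents support:

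- That longer PICU stays always score better. They do so only at equal support: 20 days with 19 ventilated scores 1, below 3 days with 1 ventilated, which scores 2.
- That the rule favours earlier death. With 4 ventilated days, death on day 5 scores 1 and on day 10 scores 6. The gap is the lack of a stated penalty for death.
- That PICU-free days could never differ between arms. Stays beyond 28 days can score negative if only the base is capped.
- That the stated 3 reveals the intended rule. Under A it needs 7 ventilated days in a 10-day stay, or a 7-day stay with 4 ventilated; the fixed count reaches it with 25 ventilated days (28 − 25 = 3). The slip may equally lie in the result.

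**Conclusion.** The concern holds, at minor severity. Without any assumption about intent, the first example is inconsistent with the stated base, the examples do not identify one definition, and no death score is stated.

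The other results depend on the natural reading. On it, PICU-free days cannot separate the arms among children with stays up to 28 days. Ventilation- and vasoactive-free days rise by one per extra PICU day at equal support, up to day 28. A child who dies can outscore a survivor with the same days of ventilation (6 against 1 in the case above). These figures assume whole-day counting and support given only in the PICU.

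The documents do not support carrying this further: the sample size, the primary and secondary analyses and the bleeding-based stopping criterion do not use free days.

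**What to change.** Before these outcomes are derived, replace the rule in Section 6.1.3 with one coherent definition and examples that follow from it. Two routes would work.

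1. Use a fixed 28-day count from surgery of days alive and off the support in question (or out of the PICU), counting days after PICU discharge as free unless support resumes and scoring death before day 28 as 0. The examples then read 24, 26 and 0. State the assumption that children discharged from hospital before day 28 are alive and free of support.
2. Keep the PICU-day base, correct the first example, state how death is scored, and report length of PICU stay instead of PICU-free days. At equal support, slower PICU discharge would still score better, so the counts should be read beside the raw durations.

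The cost is one paragraph and the derivation code. The data form is not in the documents, so whether it already holds the dates needed for the first route should be checked; record review to discharge is already planned. The first route also has a drawback: days after hospital discharge are unobserved. A child ventilated 4 days who died after discharge but before day 28 would be scored 24 instead of 0, and the documents give no rates from which to size this.
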